#### Exclusion Criteria:

- Prior diagnosis of white coat hypertension
- Prior evaluation for white-coat hypertension by 24-hr ABPM or HBPM
- Prior prescribed antihypertensive medication
- Manual office BP <140/90 mmHg
- Severely elevated office BP (systolic BP ≥ 180 mmHg or diastolic BP ≥ 110 mmHg)
- Evidence of target-organ damage (chronic kidney disease with creatinine > 1.5 mg/dL or prior history of stroke, transient ischemic attack, coronary artery disease, myocardial infarction, congestive heart failure, or peripheral arterial disease) as per electronic health record review by a medically trained chart abstractor
- **Study Type**: 2-arm parallel group cluster randomized trial

Date of First Enrollment: April 1, 2018

- Target Sample Size:8 clinics, 138 primary care clinicians
- **Recruitment Status**: Completed recruitment
- **Primary Outcomes:** Percentage of visits at which guideline-eligible patients complete out-of-office BP testing, either ABPM or HBPM,

during the 12-month post-implementation period compared to the 12-month pre-implementation period

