# To examine in a cluster randomized trial the effectiveness of a multifaceted implementation strategy at increasing out of office BP testing in adult patients with elevated office BP but no prior diagnosis of hypertension.

**Hypothesis 1a:** A greater percentage of eligible patients with elevated office BP but no diagnosis of hypertension at scheduled primary care visits at intervention clinics will complete out-of-office BP testing [primary outcome] in the post-implementation periods as compared to similarly eligible patients from control clinics

Hypothesis 1b: A greater percentage of eligible patients with elevated office BP but no diagnosis of hypertension at scheduled primary care visits at intervention clinics will have out-of-office BP ordered [secondary outcome] in the post-implementation periods as compared to similarly eligible patients from control clinics

Hypothesis 1c: A greater percentage of eligible patients with elevated office BP but no diagnosis of hypertension at scheduled primary care visits at intervention clinics will have white coat hypertension diagnosed [secondary outcome] in the post-implementation periods as compared to similarly eligible patients from control clinics

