#### Statistical Approach

Three closely related hypotheses will be used to test the effectiveness of the intervention (i.e., the multifaceted implementation strategy):

- H1: The rate of out-of-office BP testing during the post-intervention period will be higher in clinics that received the intervention than in the control clinics.
- H2: The rate of out-of-office BP testing within clinics assigned to the intervention condition will be higher during the post-intervention period than during the pre-intervention period.
- H3: The pre- to post-intervention change in the likelihood of out-of-office BP testing will be greater in the clinics that received the intervention than in the control clinics.

Multilevel Poisson regression model, where level 1 is the patient with an eligible visit and level 2 is the clinic, were used to test these hypotheses (See Appendix for details). The same approach will be used to evaluate the effect of the intervention on secondary outcomes including the rate of ABPM or HBPM test ordering.

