#### Sample Size and Power Considerations

Power calculations were based on estimates of the number of eligible patient visits and out-of-office test ordering using data from 2014, the year prior to the update to the USPSTF hypertension screening recommendations. We estimated we would have approximately 1,000 eligible patient visits during the pre-post implementation time periods. Conservatively allowing that the rate of out-of-office BP completion in the usual care clinics would increase in the years following the publication of the USPSTF hypertension screening recommendations to as high as 5% of patient visits with newly elevated office BP, we estimated the power to detect a 10% increase in out-of-office BP completion rate due to the intervention (i.e., relative risk 3.0; 15% vs 5%), at a twotailed,  $\alpha$ =0.05 significance level, for each of the 3 hypotheses described above. A multilevel Poisson regression analysis was performed on each of the 10,000 simulated datasets, and the proportion of datasets in which the null hypothesis was rejected, in the hypothesized direction, was an estimate of the statistical power to detect the assumed effect size. According to these simulations, the study has >84% power to detect the hypothesized RR=3.0 (15% completion rate in intervention clinics vs 5% in control clinics) for hypothesis H1, the comparison of post-intervention completion rates. The study also has >92% power to detect the hypothesized RR=3.0 (15% post-intervention completion rate vs 5% pre-intervention) for hypothesis H2, the test of the change in completion rate for intervention clinics only. Finally, the study has approximately 80% power to detect the hypothesized Condition\*Period interaction effect based on plausible assumptions in variation and correlation in out-of-office BP testing completion rates between clinics.

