#### **Statistical Methods**

All analyses will use the principle of intention-to-treat. Baseline patient characteristics will be examined as means (standard deviation) or percentages by randomization assignment to assess for a balanced allocation. Also, clinician characteristics will be compared across group assignment.

*Effectiveness of intervention.* The relative change, from the 12-month pre-intervention period to the 12-month post-intervention period, in the percentage of patient visits after which guideline-eligible patients complete out-of-office BP testing (either ABPM or HBPM) will be the primary outcome measured at the clinic level. This change will be estimated using a multilevel Poisson regression model(1, 2) in which level 1 is the eligible patient and level 2 is the clinic. There will be two observations for each of the 8 clinics, one for the pre-intervention and one for the post-intervention 12-month period, and each observation will include:

- 1) the outcome: the number of patients who completed out-of-office BP testing within six months of an eligible visit that occurred within the given 12-month period,
- the total number of unique eligible patient-visits during the given 12-month period (used as an "offset" variable, after log-transformation, in the Poisson regression), and
- 3) two binary predictors, Condition (0=control site, 1=intervention site) and Period (0=pre-intervention, 1=post-intervention).

The model will include two correlated random intercepts, one to capture site-specific differences (i.e., clustering by site) during the pre-intervention period and one for the post-intervention period. We considered a much more complex model that would include random effects for each individual physician, but recent work suggests that it is sufficient to model only clustering at the highest level of analysis at which clustering is assumed to occur.(3) Using a log link function, we will estimate the following model:

 $ln(OOO\_BP_{sp}) = \alpha_{sp} + \beta_1 * Condition_s + \beta_2 * Period_p + \beta_3 * Condition_s * Period_p$ (1) Where, *s* indexes clinic sites, *s* = 1 to 8,

p equals 0 for Pre-intervention period, 1 for Post-intervention period,

OOO\_BPsp equals the number of out-of-office BP assessments at site s during period p,

 $\alpha_{s1}$  equals the site specific effect for the pre-intervention period,

 $\alpha_{s2}$  equals the site specific effect for the post-intervention period, and

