 $\alpha_{s1}$  and  $\alpha_{s2}$  are assumed to have equal standard deviations,  $\sigma$ , and a bivariate normal distribution with correlation *r*.

This analysis will be used to test three closely related hypotheses:

- 1) The rate of out-of-office BP completion during the post-intervention period will be higher in clinics that received the intervention than in the control clinics. Exp( $\beta_1$  +  $\beta_3$ ) equals the relative risk (RR) of out-of-office BP assessment in intervention compared to control clinics during the post-intervention period, and testing the hypothesis that  $\beta_1 + \beta_3 = 0$  is equivalent to testing the hypothesis that this RR=1.0.
- 2) The rate of out-of-office BP completion within clinics assigned to the intervention condition will be higher during the post-intervention period than during the pre-intervention period. Exp( $\beta_2 + \beta_3$ ) equals the RR of out-of-office BP assessment in during the post-intervention period compared to the pre-intervention period, within the clinics assigned to the intervention condition, and testing the hypothesis that  $\beta_2 + \beta_3 = 0$  is equivalent to testing the hypothesis that this RR=1.0.
- 3) The Pre- to Post- change in the likelihood of out-of-office BP testing will be greater in the clinics that received the intervention than in the control clinics.  $\beta_3$ , the coefficient of the interaction term, estimates the extent to which the Pre- to Post- change in the likelihood of out-of-office BP testing is greater in the clinics that received the intervention than in the control clinics. More specifically, if RR0 equals the relative risk of out-of-office BP completion in intervention clinics compared to control clinics during the pre-intervention period and RR1 equals the relative risk during the post-intervention period, then exp( $\beta_3$ ) equals RR1/RR0, and testing the hypothesis that exp( $\beta_3$ ) =0 is equivalent to testing the hypothesis that RR1/RR0 = 1.

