Although we anticipate that the matching of clinics will have promoted balance between those clinics assigned to the intervention and control conditions, we will not incorporate the matching into the analysis. The same approach will be used to evaluate the effect of the intervention on secondary outcomes including the rate of ABPM or HBPM referrals as well as to determine maintenance of the effect of the intervention in the second year after implementation (the maintenance period).

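### Three effectiveness hypotheses carry equal standing, one of them a before-after change in intervention clinics only, and the plan does not say which contrast decides the trial

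*Combined protocol and SAP*

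**What the plan says.** Statistical Approach: "Three closely related hypotheses will be used to test the effectiveness of the intervention". The three are then listed without order. Statistical Methods repeats them as contrasts of a single multilevel Poisson model:

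- **H1**: β1+β3, intervention against control in the post period.
- **H2**: β2+β3, the rate "within clinics assigned to the intervention condition will be higher during the post-intervention period than during the pre-intervention period".
- **H3**: β3, the difference between arms in the pre-to-post change.

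Sample Size and Power Considerations is the only section that gives an alpha. It applies a two-tailed 0.05 "significance level, for each of the 3 hypotheses described above" and reports power of >84% (H1), >92% (H2) and about 80% (H3).

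The primary comparison is described in three places:

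- Registration data, Primary Outcomes: test completion "during the 12-month post-implementation period compared to the 12-month pre-implementation period". No comparison of arms is named.
- Objectives, Hypothesis 1a: more eligible intervention-clinic patients "will complete out-of-office BP testing [primary outcome] in the post-implementation periods as compared to similarly eligible patients from control clinics". This is H1.
- Statistical Methods: "The relative change, from the 12-month pre-intervention period to the 12-month post-intervention period, in the percentage of patient visits" is made the primary outcome. The text does not say whether H2 or H3 tests it.

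For other endpoints: "The same approach will be used to evaluate the effect of the intervention on secondary outcomes including the rate of ABPM or HBPM referrals". The maintenance period is handled in the same way.

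**The concern.** A cluster randomised trial earns its causal claim from the comparison between randomised arms. H1 and H3 are such comparisons. H2 is an uncontrolled before-after comparison, yet it is listed as an equal test of effectiveness and has the highest stated power. If H2 alone were significant, a network-wide rise in out-of-office testing could be credited to the implementation strategy.

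The plan takes such a rise seriously. The power section begins an assumption with "Conservatively allowing that the rate of out-of-office BP completion in the usual care clinics would increase in the years following the publication", and the Background notes similar guidelines issued in 2017.

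There is also a gap between the two valid contrasts. If H1 and H3 point different ways, the document does not say whether the trial is positive, because its descriptions of the primary comparison are not brought together.

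**Working it through.** **1. What each contrast contains.** The model in Statistical Methods gives these log rates, apart from the clinic intercepts:

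| | Pre | Post |
|---|---|---|
| Control | 0 | β2 |
| Intervention | β1 | β1+β2+β3 |

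So β2 is the control clinics' pre-to-post change. It cancels from H1 (β1+β3) and H3 (β3), and it stays in H2 (β2+β3). With no intervention effect, β3 = 0 and H2 tests β2, which is calendar time alone. This step needs no assumptions beyond the plan's model.

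**2. The plan's power figures.** They cannot be reproduced outright. The clinic SD (σ), the pre-post correlation (r), the visits per clinic and the rates assumed for H3 are not given. It is also unclear whether the roughly 1,000 eligible visits are per period or in total. What follows is a consistency check.

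Method: normal approximation on log rates with 4 clinics per arm. The variance per arm and period is 1/events + σ²/4, with pre-post clinic correlation r. Power = Φ(effect/SE − 1.96).

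Assume 125 visits per clinic-period (1,000 ÷ 8), σ = 0.41, r = 0.88 and rates of 15% and 5%. Events per arm-period are 500 × 0.15 = 75 and 500 × 0.05 = 25. σ²/4 = 0.0420 and ln 3 = 1.099.

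- H1: variance 1/75 + 1/25 + 2(0.0420) = 0.137, SE 0.371, power Φ(2.96 − 1.96) = 84%.
- H2: variance 1/75 + 1/25 + 2(0.0420)(0.12) = 0.063, SE 0.252, power Φ(4.36 − 1.96) = 99%.
- H3, assumed ratio 3.0: variance 1/75 + 3/25 + 4(0.0420)(0.12) = 0.154, SE 0.392, power Φ(2.80 − 1.96) = 80%.

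These agree with the stated >84%, >92% and about 80%. If 1,000 is the total over both periods (62.5 visits per clinic-period), H3 cannot match. Even with r = 1 its variance is 1/37.5 + 3/12.5 = 0.267, SE 0.516, power Φ(2.13 − 1.96) = 57%.

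**3. H2 when both arms rise equally and there is no effect.** The starting rate is assumed, and the end point of 5% is the plan's upper figure for usual care. With the same 125 visits, σ and r:

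- 4% to 5%: variance 1/20 + 1/25 + 0.0101 = 0.100, SE 0.316, ln 1.25 = 0.223, Φ(0.71 − 1.96) = 10.5%.
- 3% to 5%: variance 1/15 + 1/25 + 0.0101 = 0.117, SE 0.342, ln(5/3) = 0.511, Φ(1.49 − 1.96) = 32.1%.
- 5% to 5%: Φ(−1.96) = 2.5%.

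Over 62.5 or 125 visits and (σ, r) of (0.3, 0.5), (0.41, 0.88) and (0.5, 0.5), the favourable H2 rate is 6.6-10.5% from 4% and about 16-32% from 3%. H1 and H3 stay at 2.5% in this approximation.

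**4. Check with the planned model.** The Poisson mixed model was fitted to 4,000 simulated trials per setting (125 visits, σ = 0.41, r = 0.88):

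| Shared change | H2 favourable | H3 favourable |
|---|---|---|
| 5% to 5% | 2.6% | 2.8% |
| 4% to 5% | 10.5% | 2.3% |
| 3% to 5% | 33.4% | 2.4% |

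H1 was 3.9-4.8%. That excess is small-sample inflation of the Wald test, a separate matter from calendar time.

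**The case against.** The strongest reply is that the document ranks the hypotheses more than this point allows. The Objectives attach the primary outcome to Hypothesis 1a alone, which is the H1 comparison, and mark 1b and 1c as secondary. Statistical Methods puts the pre-to-post change straight into a model with a condition-by-period term, so H3 is its natural reading. A within-arm primary test would be odd in a parallel-group trial. The amendment summary also has results shown separately by arm and period, so the control-arm change would be visible beside H2.

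Much of this stands, and it limits the point. But these readings lead to two different contrasts, H1 and H3, and neither list of the three hypotheses adopts either one. Displaying the control arm does not say how H2 is to be interpreted.

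Three stronger readings are tempting and not supported:

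- *A reader might infer that H2 alone would make the trial positive, or that any one significant test would.* No section says so. The document fails to exclude it, which is different. An any-one error rate would therefore not be the plan's own error rate.
- *A reader might infer that testing did rise between the two trial periods.* None is documented. The power section allows a rise after the 2015 recommendation, and then uses 5% both for the pre period (H2) and for control clinics (H1). On those figures H2's favourable error is 2.5%.
- *A reader might infer that no ranking was ever made.* The amendment summary says the plan follows one published before any analysis. That publication may rank the hypotheses; this document does not restate a ranking.

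**Conclusion.** The point holds in a limited form. From the text and the model alone, H2 is listed as an equal test of effectiveness although it contains any shared change over time, and the document does not settle whether H1 or H3 decides the trial. Confidence in that is high.

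The size is illustrative. With no effect and a shared rise to 5%, H2 favours the intervention in about 7-11% of trials (from 4%) or 16-33% (from 3%), against 2.5% with no rise. H3 stays near 2.5%. H1 is 2.5% in the normal approximation and about 4-5% in the fitted model. The starting rate, clinic SD and correlation are assumed.

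Two further figures hold only if the 1,000 visits are per period and the H3 ratio is 3.0. At σ = 0.41 and r = 0.88, H1 and H3 disagree in about 22% of trials, and all three succeed together in about 71%. The conclusion does not depend on them.

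This should be fixed, but it does not invalidate the trial, because valid between-arm contrasts are already in the model.

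**What to change.** 1. Draw no effectiveness conclusion from H2. Report it as supportive or descriptive, beside the control-arm pre-to-post change.
2. Base the effectiveness conclusion on one between-arm contrast, H1 or H3: the one supported by the pre-analysis publication cited in the summary of changes. Report the other as supportive. If that publication already ranks the hypotheses, restate its ranking and cite it.
3. If it names none, say so, report H1 and H3 side by side with intervals, and label any choice as made after data collection.
4. Align the registration entry, Hypothesis 1a, Statistical Approach, the power section and Statistical Methods. Apply the same rule to secondary outcomes and the maintenance period.

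**Cost.** No new data or model is needed, since all three contrasts come from one fit. It is more than a wording change, however. Recruitment is complete, the post period ended in March 2019 and this version is dated March 2023, so a choice of contrast is credible only if the earlier publication supports it. Success could no longer be claimed on H2, or on whichever contrast turns out significant. H1 does not adjust for pre-period differences between clinics, and H3 has the lowest stated power (about 80%).

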#### Process evaluation

Quantitative data will be analyzed using descriptive statistics to assess reach, adoption, and implementation outcomes relevant to the intervention group. Additionally, to assess adoption, multi-level Poisson regression models will be used to compare the proportion of clinicians that referred at least one patient for out-of-office BP testing in intervention clinics versus control clinics. To assess implementation, multi-level linear regression models will also be used to compare clinician ratings of perceived barriers and facilitators (7-point Likert scales) to ordering out-of-office BP testing for guideline-eligible patients from intervention clinics versus control clinics; as in the primary analyses, clinics will be used to compare intervention clinics versus control clinics in terms of clinician reports of whether each individual intervention component was received (yes/no). Finally, an intercept-only multi-level linear regression model will be used to estimate the average "helpfulness" of the intervention, rated on a 4-point Likert scale, for intervention clinics only. Content analysis will be used to evaluate transcripts of key stakeholder interviews or focus groups, if conducted.

#### Sample Size and Power Considerations

Power calculations were based on estimates of the number of eligible patient visits and out-of-office test ordering using data from 2014, the year prior to the update to the USPSTF hypertension screening recommendations. We estimated we would have approximately 1,000 eligible patient visits during the pre-post implementation time periods. Conservatively allowing that the rate of out-of-office BP completion in the usual care clinics would increase in the years following the publication of the USPSTF hypertension screening recommendations to as high as 5% of patient visits with newly elevated office BP, we estimated the power to detect a 10% increase in out-of-office BP completion rate due to the intervention (i.e., relative risk 3.0; 15% vs 5%), at a twotailed,  $\alpha$ =0.05 significance level, for each of the 3 hypotheses described above. A multilevel Poisson regression analysis was performed on each of the 10,000 simulated datasets, and the proportion of datasets in which the null hypothesis was rejected, in the hypothesized direction, was an estimate of the statistical power to detect the assumed effect size. According to these simulations, the study has >84% power to detect the hypothesized RR=3.0 (15% completion rate in intervention clinics vs 5% in control clinics) for hypothesis H1, the comparison of post-intervention completion rates. The study also has >92% power to detect the hypothesized RR=3.0 (15% post-intervention completion rate vs 5% pre-intervention) for hypothesis H2, the test of the change in completion rate for intervention clinics only. Finally, the study has approximately 80% power to detect the hypothesized Condition\*Period interaction effect based on plausible assumptions in variation and correlation in out-of-office BP testing completion rates between clinics.

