#### Recruitment

Clinics were recruited through communications with the ACN leaders (Director of Ambulatory Care, medical directors) that could decide whether clinics should participate in the trial. These health system leaders were provided with details of the implementation strategy prior to formally enrolling in the trial.

As the intervention that the implementation strategy seeks to promote is evidencebased and considered quality improvement, a waiver of informed consent was obtained so that patients and clinicians did not need to be directly consented into the trial. For the primary analyses, we passively "enrolled" a sample of intervention group patients with elevated office BP but no diagnosis of hypertension at scheduled office visits over a 12mo pre-implementation period, and again over a 12-mo post-implementation period after a 6-mo transition period during which the multifaceted strategy was implemented, and we then "followed" each of these patients for up to 6-months after the eligible patient visit to assess for test completion. The same procedure was used to enroll control group patients from the control clinics during the pre- and post-implementation control periods.

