#### **Assignment of Interventions**

#### **Randomization and Allocation**

Clinics with similar properties were matched in pairs in terms of clinic volume of patients and clinician-training (e.g., HIV, inclusion of trainees) mix. We then randomly assigned clinics within these pairings to implementation (intervention) or usual care. Computer generated random allocation in SAS was used to assign clinics. Randomization assignment became visible to the study team only after the randomization sequence was determined. Clinicians and patients were considered unblinded to treatment allocation. Personnel who extracted and analyzed quantitative data for study outcomes were blinded. To avoid contamination during the pre-implementation period, the randomization sequence and crossover date were concealed from clinics until the start of the implementation period, and final intervention details, trainings, and marketing materials were only shared at the start of the implementation period.

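### If the 1,000 eligible visits are a total over both periods, power for the Condition × Period interaction (H3) is at most about 61%, not approximately 80%; the plan does not say what the 1,000 counts

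*Combined protocol and SAP*

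**What the plan says.** All figures are in the combined protocol and SAP, section Sample Size and Power Considerations, unless another section is named.

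- Visit count: "We estimated we would have approximately 1,000 eligible patient visits during the pre-post implementation time periods". The source is one year of data: "Power calculations were based on estimates of the number of eligible patient visits and out-of-office test ordering using data from 2014".
- Effect: relative risk 3.0, 15% against 5%, two-tailed alpha 0.05, for each of three hypotheses. H1 compares arms in the post period, H2 compares post with pre within intervention clinics, and H3 is the Condition × Period interaction.
- Power, from 10,000 simulated datasets: above 84% for H1. For H2, "The study also has >92% power to detect the hypothesized RR=3.0". For H3, "Finally, the study has approximately 80% power to detect the hypothesized" interaction effect, "based on plausible assumptions in variation and correlation in out-of-office BP testing completion rates between clinics".
- Model (Statistical Methods): multilevel Poisson regression on 8 clinics. The clinic-specific pre and post intercepts "are assumed to have equal standard deviations" (sigma) and have correlation r.
- Recruitment describes "a 12mo pre-implementation period, and again over a 12-mo post-implementation period". Randomization and Allocation adds: "Clinics with similar properties were matched in pairs in terms of clinic volume of patients".

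Visits per cell, the control pre-period rate, sigma and r are not given in this document. They may be in the reference cited for the power calculation or in the design paper named in the Summary of changes.

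**The concern.** An interaction in a two-arm, two-period design carries the sampling error of all four cells, whereas H1 and H2 each carry that of two. At the same ratio of 3.0, its power should be well below theirs. With 1,000 visits in total, the three 5% cells would each expect only about 12 or 13 completed tests. That is thin support for 80% power on an interaction.

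H3 matters because Statistical Methods names the relative pre-to-post change as the primary outcome, and H3 compares that change between arms. It is not the only candidate: Hypothesis 1a, under Objectives/Hypothesis, attaches the primary outcome to the post-period comparison between arms, which is H1. Recruitment is complete, so what is at stake is interpretation. On the total reading, a non-significant interaction could be presented as a well-powered negative when power was little better than even.

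**Working it through.** **Inputs from the plan.** 1,000 visits; 5% and 15%; two-tailed alpha 0.05; 8 clinics, 4 per arm; common sigma and correlation r.

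**Assumptions made here.** Equal cells (clinics matched on volume, two 12-month periods); control rate 5% in both periods; interaction ratio 3.0.

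**Formulas.** For n visits per cell, power = Φ(ln 3/√V − 1.96), with ln 3 = 1.0986. The cell term is 1/(np) with Poisson variance or (1−p)/(np) with binomial variance.

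- V(H1) = two cell terms + σ²/2
- V(H2) = two cell terms + σ²(1−r)/2
- V(H3) = four cell terms + σ²(1−r)

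**1. Total reading, n = 250, no between-clinic variation.** Expected events are 12.5, 12.5, 12.5 and 37.5.

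- H1 and H2, Poisson: V = 1/12.5 + 1/37.5 = 0.1067, power 92.0%. Binomial: V = 0.0987, power 93.8%. Simulation without clustering gives about 95%. The printed H1 and H2 figures are therefore attainable.
- H3, Poisson: V = 3/12.5 + 1/37.5 = 0.2667, √V = 0.5164, power = Φ(2.127 − 1.960) = 56.7%.
- H3, binomial: V = 0.2507, √V = 0.5007, power = Φ(2.194 − 1.960) = 59.3%.

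**2. Ceiling on the total reading.** Dividing the 1,000 visits so as to minimise V(H3) gives 58.4% with Poisson variance (28/28/28/16%) and 61.3% with binomial variance (28.2/28.2/28.2/15.4%). No split does better. The term σ²(1−r) cannot be negative, so no values of sigma and r raise these figures.

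**3. Effect of clustering on the total reading.** For assumed sigma 0.2–0.4 and r 0.5–0.95, H3 is 46–56% (Poisson). Simulating the planned model with 63 visits per clinic-period (1,008 in total), sigma 0.32 and r 0.85 gives H1 86%, H2 92% and H3 54%.

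**4. Visits needed for 80% without clustering.** V must fall to (1.0986/2.8016)² = 0.1538. The total is then 266.67/0.15377 = 1,734 visits (Poisson) or 250.67/0.15377 = 1,630 (binomial).

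**5. Per-period or per-arm reading, n = 500.** With no clustering, H3 is 85.3% (Poisson). With sigma 0.41 and r 0.88, σ²(1−r) = 0.1681 × 0.12 = 0.0202:

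| | V | Power by formula |
|---|---|---|
| H1 | 0.0533 + 0.0841 = 0.1374 | 84% |
| H2 | 0.0533 + 0.0101 = 0.0634 | 99% |
| H3 | 0.1333 + 0.0202 = 0.1535 | 80% |

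Simulating the planned model at these values gives H2 99.2% and H3 about 83% with a Wald test, or H2 97.5% and H3 78% with a likelihood-ratio test. All three printed figures can be met on this reading.

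**6. Control pre-period rate.** Among rates up to 5%, 5% is the favourable choice. At 4%, with the other rates unchanged, the interaction ratio is 3.0/1.25 = 2.4 and H3 falls to 37% at n = 250.

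**The case against.** The strongest reply is that no contradiction is proved. The visit estimate comes from a single year and each period is planned as 12 months, so 1,000 per period is a fair reading. A per-arm reading gives the same 500 per cell. This stands: on either of those readings every printed power is attainable, and the plan needs only clearer wording.

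A reader might go further and infer that the H2 and H3 figures clash whatever 1,000 means, since H3 at 80% goes with H2 of roughly 97–99%. The documents do not support that. The H1 and H2 powers are printed as lower bounds, and 99% satisfies a bound of 92%. Nor does the close fit of H1 and H2 to the total reading show that a total was meant. At 500 per cell and sigma 0.41, H1 is 84% whatever r is, and H2 exceeds 92% for every r from 0.37 up.

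The missing inputs may also be in the cited sources. Those could settle what the 1,000 counts. They could not rescue the total reading, because 61% is already the value with no clustering and the best split.

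Finally, H1 may be the operative primary comparison. That limits the consequence, but H3 is still listed as an effectiveness test with its own stated power.

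**Conclusion.** The point holds conditionally. On the plain reading of the visit count as a total, H3 power is about 57–59% without between-clinic variation, at most about 61%, and lower with clustering. The printed approximately 80% would need some 1,630 to 1,734 visits. On a per-period or per-arm reading there is no error in the printed powers, only an unclear count.

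The result rests on an interaction ratio of 3.0 and a control rate flat at 5%; the 57–59% figures also assume equal cells, while the 61% ceiling covers any split. The formula is a large-sample one, but simulation on the total reading agrees closely for H3.

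A reader might infer that the trial as a whole is underpowered. The documents do not support that: the stated H1 power is attainable on every reading considered. The point should be fixed because it decides what a null interaction can be taken to mean. Confidence is medium, since the arithmetic is firm and the reading of the count is open.

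**What to change.** State whether 1,000 is the total, per period or per arm. Rerun the existing simulation and report H1, H2 and H3 power from one stated set of inputs: visits per cell, all four completion rates, sigma and r. Copy these from the cited source if they are recorded there.

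- If 1,000 is the total: replace the H3 power with the rerun figure, expected to be about 60% or lower. Report the interaction with its 95% confidence interval, and do not describe a null result as a well-powered negative.
- If 1,000 is per period or per arm: correct the wording of the count. Restating the H1 and H2 powers is then optional.

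The cost is one rerun and one revised paragraph, with no new data and no change to the design, model or tests. The downside is that on the total reading the stated H3 power becomes less favourable.
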